11.16 PARENT-PATIENT DYAD INTERVIEW GUIDE PRE-INTERVENTION **ERROR! BOOKMARK NOT DEFINED.**

11.17 PARENT-PATIENT DYAD INTERVIEW GUIDE Post-INTERVENTION **ERROR! BOOKMARK NOT DEFINED.**

11.18 PEDIATRIC CARDIAC CRITICAL CARE CONSORTIUM (PC⁴) VARIABLES ... **ERROR! BOOKMARK NOT DEFINED.**

ABBREVIATIONS AND DEFINITIONS OF TERMS

AHD	Advanced Heart Disease
CAT-T	Communication Assessment Tool-Team
CHOP	Children's Hospital of Philadelphia
CICU	Cardiac Intensive Care Unit
CPS-P	Control Preferences Scale for Pediatrics
CSACD	Collaboration and Satisfaction About Care Decisions
CST	Communication Skills Training
FCC	Family-centered Care
HAD	Hospital Anxiety and Depression Scale
ICU	Intensive Care Unit
IES-R	Impact of Event Scale-Revised
IOM	Institute of Medicine
IPE	Interprofessional Education

MIPS	Medical Interaction Process System
PC ⁴	Pediatric Cardiac Critical Care Consortium
PERCS	Program to Enhance Relational and Communication Skills
PFS-ICU 24	Pediatric Family Satisfaction with Care in the Intensive Care Unit
PPCS	Pediatric Palliative Care Specialists
PTSD	Post-traumatic Stress Disorder
SDM	Shared Decision-making

ABSTRACT

Context:

A large proportion of children with advanced heart disease (AHD) die in the pediatric cardiac intensive care unit (CICU), where parents describe obtaining a realistic understanding that their child had a life-limiting disease only 2 days prior to death. Delayed or inadequate communication within teams or with families may contribute to this lack of understanding (as shown in children with other serious illnesses), while interactions with pediatric palliative care specialists (PPCS) have been shown to improve communication and understanding of prognosis. The limited number of PPCS, however, means that all clinicians in the CICU must have the skills to support parental decision-making, including giving bad news and eliciting parental goals for their child.

Objectives:

1. To develop a communication skills training (CST) program for interprofessional teams in the pediatric CICU via a co-design process.
2. To evaluate CICU clinicians' perceived feasibility and acceptability of the CST.
3. To evaluate CST impact on communication skills and team function in actual family meetings.
4. To learn parents' perspectives about communication challenges in the CICU.
5. To determine the parents' perceived acceptability of the parent-facing aspects of the CST program.
6. Evaluate clinician fidelity to intervention plan.

Study Design:

Cohort study with pre and post assessments around an intervention.

Setting/Participants:

Clinicians at CHOP and parents of children previously hospitalized in the ICU will be invited to participate in the co-design portion of the study. A separate group of volunteer attending intensivists, cardiologists, cardiac surgeons, front line clinicians, nurses, and social workers from the pediatric CICU at the Children's Hospital of Philadelphia (CHOP) will undergo the CST program intervention and participate in observed family meetings. Other clinicians who are participating in an observed family meeting will also be enrolled. Parents or legal guardians and their children in the CICU who have been there for at least 7 days and are expected to stay at least another 7 days will also be consented and enrolled.

Study Interventions and Measures:

Intervention:

The intervention is a CST for a group of interprofessional clinicians that will include practice in communication skills of giving bad news and eliciting goals of care and building team collaboration. Parental-facing aspects of the intervention include parental preparation

for family meetings and provision of written summary of the family meeting after its completion.

Measures:

The Co-design process to develop the intervention will have focus groups to evaluate the interventions' content and feasibility and a survey to measure participant engagement in the focus groups.

The impact of the CST program on CICU clinicians' perceived usefulness and satisfaction with the training will be measured with a post-CST survey. This survey will also measure clinician burnout, demographics and experience with modalities of communication pre and during the COVID-19 pandemic. Furthermore, a random sample of 8 clinicians participating in the CST will complete an acceptability interview regarding their thoughts on the intervention.

For the actual family meetings, assessment of the impact of the CST on communication and team function in actual family meetings pre and post-CST will be done by coding audio recordings using the same tools as in simulated encounters and qualitative coding of content. Collaboration will be measured using the amount of time different members of different disciplines speak, and team member perception and satisfaction with collaboration will be measured using a validated tool.

Parents' experiences in family meetings and perspectives on communication with the clinical team will be measured with a pre-intervention survey or interview. Parents' acceptability of the parent preparation process for the family meeting and of the written summary received after the meeting will be measured during the post-intervention survey and interview.

TABLE 1: SCHEDULE OF STUDY PROCEDURES

Clinicians and Parents Participating in Co-design		
Study Phase	Enrollment	Co-design
Visit Number	1	2-12
Study Days	1	2-400
Enrollment	X	
Get Feedback through Focus Group		X
Measure Engagement through Survey		X

Clinicians Participating in Intervention				
Study Phase	Enrollment	Intervention	Follow-up	
Visit Number	1	2-11	5-30	6-21
Study Days	1	2-200	9-500	36-310
Enrollment	X			
Communication Skills Training (up to 10 hours)		X		
Online course evaluation survey including Maslach burnout score and COVID-19 questions		X		
Post-CST actual clinical encounters			X	
Follow-up actual meeting survey			X	
Acceptability interview				X

Clinicians Not Participating in Intervention		
Study Phase	Enrollment	Pre or Post-Intervention
Visit Number	1	2-17
Study Days	1	2-540
Enrollment	X	
Observed Family Meeting		X
Online Survey		X

Parent-patient Dyads Participating in the Survey (Prior to Intervention)		
Study Phase	Enrollment	Follow-Up
Visit Number	1	
Study Days	1	2-730
Enrollment	X	
Online Survey	X	
Medical record review (patient or family not contacted)		X

Parent-patient Dyads Participating in the Interview (Prior to Intervention)		
Study Phase	Enrollment	
Visit Number	1	
Study Days	1	
Enrollment	X	
In-person Interview	X	

Parent-patient Dyads Participating in the Survey and Interview (After Intervention)					
Study Phase	Enrollment	Follow-Up	Follow-Up	Follow-Up	Follow-Up
Visit Number	1	2	3	4	
Study Days	1	1-10	1-60	2-60	2-730
Enrollment	X				
Recording of Family Meeting		X			
Online Survey			X		
Interview				X	
Medical record review (patient or family not contacted)					X

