Potential subjects will be screened using the protocol inclusion and exclusion criteria. Parent-patient dyads will be recruited into the study in person, over the phone, or via e-mail. The goal for enrollment will be up to 50 parent-patient dyads, with 30 evaluable parent-patient dyads. Parent-patient dyads who are enrolled in the post-intervention follow-up phase will be asked for access to information entered into the REDCap based Family Meeting Worksheet if they choose to use it, will be given an online survey in person or via e-mail to obtain post-intervention data assessing parental satisfaction, understanding, trust in the clinical team, emotional well-being and parents' acceptability of the parent-facing elements of the intervention, which includes preparation for the meeting and their perception of the written summary after the family meeting. Medical record review of this group of parents will utilize EPIC and the PC⁴ database, but will not require patient or parent involvement. A subset of enrolled patient-parent dyads will also be invited to participate in an interview assessing parents' acceptability of the parent-facing elements of the intervention.

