- *Parental feelings about communication with the clinical team:* myICU¹¹⁹ is an 11 item tool adapted by the authors of the tool to assess a surrogate’s perceptions of how comfortable the surrogate feels discussing potential concerns they have with their child’s medical team regarding their child’s care in the ICU.
- *Parental involvement in other family meetings*
- *Fidelity of Parent Preparation and Acceptability:* Parents will be surveyed on whether they were given the Family Preparation Worksheet and whether clinicians followed up on how they used the worksheet. They will be asked what they thought of the worksheet. They will also be asked about their acceptability of the Family Meeting Summary Worksheet. The use and acceptability survey was adapted from a Shared Decision Making tool.¹²⁰ See Appendix 11.15 for specific items.
- *Medical record review:* Patient data will be retrieved from Epic and PC⁴ national database registry. Data listed below are main patient record variables. See Appendix 11.18 for full list of PC⁴ variables
 - Child’s name
 - Child’s MRN#

- Child's date of birth
- Child race/ethnicity
- Parent/legal guardian race
- Parent/legal guardian contact number
- Parent/legal guardian e-mail address
- Parent/legal guardian address
- Length of stay in the CICU
- Length of stay in the hospital
- EPIC Problem List
- Medication list and administration dates throughout hospitalization
- Limitations of interventions during study period
- Date of limitations of interventions during study period
- ICD-9 codes associated with hospitalization
- Date of discharge from CICU / Date of death/ discharge from hospital
- Discharge disposition from CICU and hospital (floor / home / rehab facility / palliative care / hospice)
- Palliative care consult
- Ethics consult
- Gestational age
- Fundamental Cardiac Diagnosis
- Chromosomal abnormalities
- Syndromes
- Cardiothoracic surgery and date
- Primary insurance type
- Discharge 30 day mortality status
- Number of prior cardiothoracic operations
- Reason for CICU encounter
- Non-cardiothoracic surgery
- Encounter cardiothoracic diagnosis
- Encounter medical diagnosis
- DNR/DNI on file
- Withdrawal of life sustaining therapy
- Bleeding requiring reoperation and date
- Unplanned reoperation/reintervention and date
- Sternum left open and date
- Cardiac arrest and date
- Stroke and date
- Risk group as measured by the STAT mortality category
- operative or post-operative complications

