Parent-patient Dyads Participating in the Survey or Interview Prior to Intervention: We will identify via medical record screening patients who have been admitted to the CICU for at least 7 days and are expected to stay for at least another 7 days and whose parents are therefore eligible for participation in a complex care family meeting. Parent-patient dyads will be approached in person by a member of the research team to consent to participate in the study or will be called to determine when they will next be present in the CICU for further discussion of the study. Up to 100 parent-patient dyads for the survey and 30 parent-patient dyads for the interview will be consented and enrolled with the expectation that we will achieve 95 evaluable parent-patient dyads for surveys and 23 evaluable parent-patient dyads for interviews.

Parent-patient Dyads Participating in the Survey or Interview After Intervention: We will identify via medical record screening patients who have been admitted to the CICU for at least 7 days and are expected to stay for at least another 7 days, or the patient has already been admitted to the CICU 14 days and whose parents are therefore eligible for participation in a complex care family meeting. Parent-patient dyads will be approached in person, over the phone or via e-mail by a member of the research team to consent to participate in the study or will be called to determine when they will next be present in the CICU for further discussion of the study. Up to 50 parent-patient dyads will be enrolled for, with a goal of 30 evaluable patient-parent dyads for the survey. Up to 25 parent-patient dyads (of the 50 enrolled for the survey) will be invited to be interviewed in the post-intervention, with a goal of 15 evaluable parent-patient dyads.

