8.6.1 Selecting Family Meetings

Working with several CICU team members, we will identify family meetings that are scheduled. We will confirm with the primary team planning the family meeting which family members are likely to be present and we will contact them either via phone, in person or via e-mail to discuss the study. We will also confirm with the primary team who the other clinicians are that are likely to be present in the meeting and we will contact them either via email or in person to discuss the study.

When audio or video recording participating clinicians during actual family meetings, others present at the meeting will be recorded as well. This will include parents, patients, and

clinician team members participating in an observed family meeting who did not undergo the CST (because they were not eligible, did not wish to participate in the study, or were not approached because sufficient clinicians were already enrolled).

Parent-Patient Dyads Prior to the Intervention

During recruitment within the CICU in-patient units, a member of the research team will approach parents and patients who will be participating in an observed family meeting in the patient room, or over the phone if the parents will not be in the CICU prior to the family meeting and provide information about the study. A member of the study team will present a one-page explanation of the study to the parents. The explanation will cover the purpose of the study, procedures, risks and benefits of participation, what information will be collected, contact information for study personnel, that their private information will not be written down or used, and that parents can opt-out at any time.

Patients who are 18 years old and will be present in the audio recorded family meeting will be allowed to opt-out as adults if they are medically and cognitively capable of comprehending study purposes and can decline participation.

Parent-Patient Dyads After the Intervention

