During recruitment within the CICU in-patient units, a member of the research team will approach parents and patients who will be participating in an observed family meeting in the patient room, or over the phone, or via email if the parents will not be in the CICU prior to the family meeting and provide information about the study. A member of the study team will consent the parents prior to study procedures would begin. The explanation will cover the purpose of the study, procedures, risks and benefits of participation, what information will be collected, contact information for study personnel, that their private information will not be written down or used, and that parents can opt-out at any time.

Patients who are 18 years old and will be present in the audio or video recorded family meeting will be allowed to opt-out as adults if they are medically and cognitively capable of comprehending study purposes and can decline participation.

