## Statistical Analysis Plan

Aim 2: Pilot test the co-design-adapted CICU TALC with CICU parents and clinicians to determine:

a) Acceptability of intervention: Hypothesis: Respondents will endorse above a critical threshold of acceptability on satisfaction instruments to 20 clinicians and 23 parents and in semi-structured interviews.

Analytic plan: A constructivist grounded theory approach will guide qualitative analysis of interview transcripts regarding acceptability of the intervention. Descriptive statistics will be calculated for quantitative data from the acceptability survey.

b) Feasibility of enrollment and data collection, and fidelity: Hypothesis: Feasibility will be defined by: i) 30% parental and 50% clinician enrollment and consent rates, and 80% subject retention, and attrition; ii) ability to collect outcomes data from 46 patients (CICU length of stay), from 46 parents and from 50% of eligible team members. and iii) intervention fidelity with 95% of enrolled parents and clinicians receiving parent-directed and team-directed interventions.

Analytic Plan: Data completeness and accuracy will be monitored. I will calculate descriptive summaries including means and standard deviations for continuous variables, and proportions for categorical variables. As appropriate for pilot trials, analyses will focus on estimating proportions of binary feasibility and fidelity endpoints and constructing 95% CIs. Analyses of parent-reported outcomes will primarily be descriptive. Means and standard deviations along with 95% confidence intervals will be calculated.

c) Impact of CICU TALC on CICU parent and team behavior in family meetings. Hypothesis: the intervention will increase parent speaking time by 60%, elicitation of parental concerns to 40%, and response to parental emotion by 30%. I will audio record 230 CICU family meetings occurring before CICU TALC is initiated and 230 after initiation and use quantitative methods to measure pre-vs-post differences in a) speaking time of parents and physicians; b) elicitation of parental concerns; and c) response to parental emotion.

Analytic Plan:

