- Speaking time will be analyzed by comparing the change in the number of words spoken by physicians versus parents speak in pre- and post-CICU TALC meetings using generalized linear regression with binomial link function controlling for the length of the meetings. Means and standard deviations will be calculated for the tool and t-tests will determine if significant differences exist for the two groups pre and post-CICU TALC.
- Elicitation of parental concerns and empathic response to parental emotion will be determined through quantitative coding. Each skill will be analyzed separately, using the cutoffs to identify skill proficiency as used by Back. Univariate relationship pre/post intervention by outcomes (Table 1)
  - If the outcomes (skills acquisition scores) are continuous and satisfies the normality assumptions, then t-tests will be appropriate to compare pre – intervention and post – intervention changes.

- If outcomes are continuous but not normally distributed, then a Wilcoxon Rank sum test will be appropriate to compare pre –intervention and post –intervention changes.
- If outcomes are binary (high vs low), then chi-square/fishers exact tests will be appropriate to compare pre –intervention and post –intervention changes.
- Similar statistical analysis will be performed to compare pre –intervention and post –intervention changes overall and for each type of participant.
- Analyses will be presented at the meeting-level as well as the participant-meeting level. Participant-meeting level data will be stratified by physician-type pending  $\geq 5$  participants in the pre- and post-intervention groups for each type.
- Relationship pre/post intervention by outcomes adjusted for participant and meeting level characteristics
  - If sample size allows and there are significant univariate associations, we will utilize mixed effect regression models to explore the relationship between the intervention and outcomes, first controlling for--gender and years of experience and accounting for correlation of repeated measurements within participants. If sample size allows, we will include other characteristics including number of participants at the meeting, proportion of speaking time by participant type, etc

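### The SAP's 230 post-initiation meetings conflict with the Protocol's roughly 28 meetings, 50-dyad cap and single recording visit; if families are recorded more than once, the main tests ignore family correlation

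*Protocol*

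**What the plan says.** The documents give several incompatible pictures of how many meetings will be recorded and from how many families.

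- **SAP, Aim 2c:** "I will audio record 230 CICU family meetings occurring before CICU TALC is initiated and 230 after initiation". No derivation of the 230 is given.
- **Protocol 3.1.5:** about 28 post-training meetings, so that each discipline appears in 23. Section 3.1 asks for at least 23, and section 6.4 for at least 20 encounters before and after. Section 3.3.2 stops at 56 per discipline, which is twice 28.
- **Protocol 3.1, dyads after the intervention:** "The goal for enrollment will be up to 50 parent-patient dyads, with 30 evaluable parent-patient dyads". Section 8.5 repeats it: "Up to 50 parent-patient dyads will be enrolled for, with a goal of 30 evaluable patient-parent dyads for the survey".
- **Protocol Table 1, dyads after the intervention:** one row, "Recording of Family Meeting", marked once, at Visit 2.
- **Protocol 8.6.1, after the intervention:** "A member of the study team will consent the parents prior to study procedures would begin". Recorded post-phase families are therefore consented families.
- **Protocol 8.6.1, both phases:** "Working with several CICU team members, we will identify family meetings that are scheduled". No limit of one meeting per family is stated. Pre-phase parents receive a one-page explanation and may opt out; their recording is not tied to the enrolled survey or interview dyads.

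On analysis, the SAP says "Analyses will be presented at the meeting-level as well as the participant-meeting level". It names a generalized linear model for speaking time, plus t, Wilcoxon rank-sum and chi-square or Fisher tests. None has a cluster term. A mixed model allowing for repeated measurements within participants follows only if numbers permit and the unadjusted result is significant. Protocol 6.3.2 and 6.4 adjust for the individual clinician. Neither document names the family or patient as a cluster.

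**The concern.** Aim 2c compares parent and physician speaking time, elicitation of parental concerns, and response to parental emotion. All three depend at least partly on who the parents are. A second recorded meeting with the same talkative or distressed family repeats some of the information in the first.

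If families recur and the test counts each meeting as new, the standard error is too small and the nominal 5% level is not kept. The unadjusted test also decides whether the mixed model is fitted at all, so the error enters at the first step. An imbalance in repetition between phases would also let repeat families weigh more heavily on one side of the comparison.

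Repetition is plausible. Eligible children have long CICU stays, and the parent measures in Protocol 5.1.1 include "Parental involvement in other family meetings". That item shows that families may attend several meetings; it does not show that several are recorded.

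**Working it through.** **1. Can the 230 be reproduced?** No. Aim 2c gives no baseline rate, SD, power or ICC. For elicitation rising to 40%, a two-sided 5% test with 80% power needs about 230 per period only if the baseline is about 27.5% to 27.8%, a rate the documents do not state.

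**2. Do the counts agree?**

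- 230/28 = 8.2 and 230/23 = 10, so the SAP figure is about 8 to 10 times the Protocol's.
- One recording per dyad with at most 50 dyads gives at most 50 post-phase recordings, not 230.
- 230/50 = 4.6 meetings per family at the cap, and 230/30 = 7.67 with the 30 evaluable dyads.
- 28/50 = 0.56 and 28/30 = 0.93, so at the Protocol's size no post-phase family need appear twice.

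Either 230 is unreachable under Table 1, or post-phase families are recorded repeatedly.

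**3. Cost of ignoring family if 230 stands.** Inputs: 230 meetings per phase (SAP), 50 post-phase families (Protocol), hence m = 4.6. Assumptions: family ICC 0.1 to 0.5, equal numbers of meetings per family, one meeting per family in the pre phase.

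- Design effect: DE = 1 + (m − 1) × ICC = 1 + 3.6 × ICC
- Effective post-phase n = 230/DE
- Factor by which the true standard error of the pre-post difference exceeds the one used: F = √((1 + DE)/2)
- True two-sided level = 2 × (1 − Φ(1.96/F))

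| ICC (assumed) | DE | Effective n (post) | F | True level of a 5% test |
|---|---|---|---|---|
| 0.1 | 1.36 | 169 | 1.09 | 7.1% |
| 0.2 | 1.72 | 134 | 1.17 | 9.3% |
| 0.3 | 2.08 | 111 | 1.24 | 11.4% |
| 0.5 | 2.80 | 82 | 1.38 | 15.5% |

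Simulated two-sample t-tests with no true effect gave 7% to 16% over the same range.

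**4. Sensitivity to the pre phase.** The documents do not say how many pre-phase meetings come from each family. If both phases were clustered equally (an assumption), F = √DE and the true level would be 9.3% at ICC 0.1 and 24.1% at ICC 0.5.

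**5. One meeting per family in both phases.** With m = 1, DE = 1 at any ICC, and the level stays at 5%.

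**6. Do the planned adjustments cover family?** The first covariates of the SAP's mixed model are gender and years of experience. Protocol 5.1.1 collects years in practice for clinicians and lists no such item for parents, so "participants" there appears to mean clinicians. A clinician term, in either document, does not absorb correlation between meetings of one family attended by different clinicians.

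**The case against.** A reader might infer that the intervals for these outcomes are simply too narrow. The documents do not support that as a fact. Table 1 shows one recording per post-phase dyad, and the Protocol's roughly 28 meetings fit within 30 to 50 dyads without repetition. On that reading the post phase has no family clustering. The 230 has no derivation. The SAP's use of 23 and 46 elsewhere in Aim 2 makes a slip for 23 possible, but nothing settles it.

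Four further objections carry some weight.

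- No passage says that any pre-phase family is recorded twice. The absence of a limit permits repetition but does not establish it.
- The SAP's word for the clustering unit is ambiguous. It uses the same word in discussing types of participant and their share of speaking time, so parents might be included. Even so, that model is conditional and the main tests are not.
- The SAP treats elicitation and empathic response as clinician skills, so their family ICC may be lower than that of parent speaking time. The upper end of the assumed range need not apply to all three outcomes.
- This is a pilot with a qualitative primary endpoint, and these comparisons are secondary.

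These objections make the loss of precision conditional. They do not remove the conflict of counts or supply a rule for families who recur.

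**Conclusion.** The point holds in conditional form. The SAP's 230 cannot be squared with the Protocol's roughly 28 meetings, the 50-dyad cap and the single recording visit. If 230 is kept, post-phase families must average at least 4.6 meetings each, and the main tests as written would overstate precision. At an assumed family ICC of 0.1 to 0.5, the pre-post standard error should be 1.09 to 1.38 times the one used, and the false-positive rate is about 7% to 16% with clustering in the post phase only. The size rests on that ICC, which the documents do not give, and on equal numbers of meetings per family. If every family is recorded once in each phase, nothing is lost. The plan should be changed, because it neither rules out repeated families nor allows for them in its main tests.

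**What to change.** 1. Reconcile the SAP's 230 with the Protocol's meeting counts, the 50-dyad cap and Table 1. State in both documents how many meetings, from how many families, are expected in each phase.
2. Then choose one rule and write it into the SAP. Either analyse only the first recorded meeting of each family, or attach an anonymous family code to every recording and use family-clustered standard errors or a family random intercept. Apply the chosen rule to the main comparisons of speaking time, elicitation and empathic response, alongside the clinician term and not only after a significant unadjusted test.
3. Report families and meetings per family by phase. If repeats are kept, add a sensitivity analysis on each family's first meeting.

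For new recordings the cost is one code each and some SAP wording. Intervals will widen where families repeat. Existing pre-phase recordings may be harder: sections 3.2 and 8.1.1 suggest that some predate the COVID pandemic, and section 8.6.1 assures parents that private details are not noted, so linkage may be incomplete and should be reported as such. If the post phase is one meeting per family, a random intercept cannot be separated from residual error there; clustered standard errors or the first-meeting analysis are then the simpler choice.
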